4. **Antibiotic use:** Antibiotics are not required in low risk patients undergoing laparoscopic cholecystectomy, but may reduce the incidence of wound infection in high risk patients (age > 60 years, the presence of diabetes, acute colic within 30 days of operation, jaundice, acute cholecystitis, or cholangitis) [12].
5. **Use of drains:** drains are not needed after elective laparoscopic cholecystectomy and their use may increase complication rates; however, they may be useful in complicated cases particularly if choledochotomy is performed [12].
6. **Bile Duct Injury (BDI):**
 - a. If major BDI occur, outcomes are improved by early recognition and immediate referral to experienced hepatobiliary specialists for further treatment before any repair is attempted by the primary surgeon, unless the primary surgeon has significant experience in biliary reconstruction [7,8,12].
 - b. If considering all types of BDIs, rates are 0.4% and 0.8% for elective and emergency settings, respectively [7].
 - c. It is recommend knowing Strasberg's classification, which remains the most commonly used classification for BDIs [7].

Post-operative

1. **30-day readmission:** rate should be <10% [11].
2. **Critical care:** There should be access to critical care beds (both level 2 and level 3) with on-site renal support [11].

OVERVIEW OF STUDY DESIGN

GECKO is a prospective, international, multicentre, observational cohort study delivered by GlobalSurg Collaborative. This will be on consecutive patients undergoing cholecystectomy, between 31st July 2023 to 19th November 2023, with follow-up at 30-day and one-year postoperatively. Mini-teams of up to five collaborators ([see page 17](#)) per 14-day data collection period will prospectively collect data at each participating centre.

GLOBALSURG COLLABORATIVE

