GlobalSurg (<http://globalsurg.org/>) is a collaboration between practising surgeons from around the world, performing research in surgery to foster local, national and international research networks. The collaborative model used has previously been described elsewhere [13] and has already facilitated three multicentre, international, prospective cohort studies including a total of 46,186 patients undergoing emergency and elective abdominal surgery [14-16]. The NIHR Unit on Global Surgery was established in 2017 and is a consortium between the Universities of Birmingham, Edinburgh and Warwick, together with international partners. The unit's objective is to advance the education of medical students and doctors in surgical science, clinical research and audit methods by promoting participation in collaborative clinical research and audit studies.

STUDY SETTING

The study is open to any hospital worldwide that performs emergency and/or elective cholecystectomy. An eligible hospital must collect consecutive patients undergoing cholecystectomy during the specified study period, following appropriate registration of the study according to local hospital regulations.

Included centres should ensure data collection is >90% complete. Centres with >10% missing data, when including all data points, will be excluded from the final analysis and removed from the authorship.

There is no minimum number of patients per centre, as long as all eligible patients treated during the study period are included.

STUDY POPULATION

Summary

The study population includes consecutive patients, admitted to hospital within the pre-specified data collection periods, undergoing cholecystectomy as the index operation.

Inclusion Criteria

- **Age:** All adult patients (greater than or including 18 years of age).
- **Procedure:** Primary cholecystectomy, where this is the main procedure planned.
- **Approach:** Open, laparoscopic (standard and single-port), and robotic. Gasless laparoscopic and robotic approaches are included. Laparoscopic and robot converted cases are also eligible.
- **Urgency:** Elective, delayed and emergency procedures.

Exclusion Criteria

- **Procedure:** Patients having a cholecystectomy as a part of another surgical procedure; for example, Whipple's procedure, bariatric, anti-reflux, or transplant operations, should be excluded.
- **Indication:** Patients with Mirizzi syndrome should be excluded.

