- **Return to theatre:** Each patient should only be entered into the study once. Any patient returning to theatre and requiring a cholecystectomy for whatever indication, should not be included.
- **Known gallbladder malignancy:** when the diagnosis of gallbladder cancer is established pre-operatively, the patient should be excluded. However, if gallbladder cancer is found unexpectedly during or after cholecystectomy (i.e. on histology), the patient should be included.

STUDY PROCEDURES

Site Survey

In order to describe local processes and resources, each site will be asked to complete an online site survey questionnaire to delineate the variation of cholecystectomy services and training amongst included hospitals (**Appendix C**).

*Completion of the short site survey can be done by a supervising consultant (preferred) or a hospital lead trainee that is familiar with the cholecystectomy practices at your site. Completion of the site survey is necessary before the site is granted access to the online **GECKO**: Data Collection form.*

Data Collection

Collaborators will collect data on consecutive eligible patient undergoing cholecystectomy within the pre-specified data collection periods (**Table 1; page 15**). Data collectors should use a combination of the **GECKO** Case Report Form (**Appendix A**) alongside the Data Dictionary (**Appendix B**) to successfully record required data on all eligible patients. Collaborators will create clear mechanisms appropriate to their institution to identify and include all eligible patients, involving daily review of operating logbooks, multidisciplinary team meeting, admission and handover lists. Local arrangements may include daily review of the patient and notes focused on included data points.

Data will be collected and stored online via the Research Electronic Data Capture (REDCap) web application (**see pages 20-21**), hosted and managed by the University of Edinburgh, United Kingdom. No patient identifiable data will be uploaded or stored on the REDCap database.

Strategies to identify consecutive eligible patients could include:

- *Daily review of elective theatre lists.*
- *Daily review of handover sheets/emergency admission and ward lists.*
- *Daily review of theatre logbooks (both elective and emergency).*

Follow-up Period

Centres will undertake patient follow-up at two timepoints:

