Validation by primary data collection teams:

- Follow-up methodology at patient level: all hospitals will self-report the methods used to determine 30-day outcomes.
- Patient identification methodology: all hospitals will self-report the methods used to identify patients who fulfil the inclusion criteria.

Validation by independent teams:

- Case ascertainment: hospital records will be reviewed to identify patients fulfilling the inclusion criteria within a 2-week data collection period and comparing this to the actual number of cases submitted. This will be performed by individuals not involved in collecting the primary data. By comparing samples, a quantitative estimate of case ascertainment will be produced by the central data team.
- Data accuracy: a subset of collected variables will be validated by individuals who are independent of the primary data collection process. Following the “case ascertainment” stage, validators will be asked to provide data for a subset of variables, two patient variables, two operation variables, and two outcome measures.

Project Team Structure

Each registered centre must have a supervising consultant/attending to ensure adequate data quality. In the case that the hospital lead is a registrar/resident then they must recruit a consultant/attending to supervise the study. The hospital lead should also ensure that they recruit independent data validators (registrars/residents or consultants/attendings) to perform the data validation outlined in the section above.

For data collection, the hospital lead should recruit a “mini-team” of up to five local collaborators for each data collection period (**Table 1; page 15**). Medical students, doctors (non registrars/residents or consultants/attendings) and nurses can act as local collaborators and their participation is encouraged. The same “mini-team” can cover different time periods at each hospital if they wish to. Each team should include at least one qualified doctor to provide additional local support for participating medical students or nurses. Additional collaborators can be recruited to aid one-year follow-up data collection once the follow-up period begins (31st Jul 2024). A detailed specification of each role can be found below (see **pages 23-24**).

STATISTICAL CONSIDERATIONS

Primary Outcome Measure

The primary endpoint of this study is the compliance to pre-, intra-, and post-operative audit standards (see pages 9-10).

Secondary Outcome Measures

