Further prespecified subgroup analyses will be made by operative approach (open, laparoscopic and converted), and operative urgency (elective, emergency and delayed surgery). Audit standards (see pages 9-10) and site survey (Appendix C) will guide exploratory analysis into the global variation in the provision of cholecystectomy and available resources. However, it is acknowledged that some audit standards are designed for high-income settings and therefore their attainment will not be considered mandatory or a potential definitive measure of quality in global cholecystectomy.

Identification of hospital or surgeon-specific performance will not be reported. Following analysis, results will be fed back to participants at the centre level, but no other centres will be identifiable.

Based on previous GlobalSurg studies [14-16], GECKO is anticipated to include around 500 centres globally. With consideration to recent figures provided by previous collaborative studies [3,5] on cholecystectomy, a sample of approximately 15000 patients is anticipated. The recent multi-society practice guidelines on prevention of bile duct injury [8] advised that a study adequately powered to detect and report on bile duct injury would require at least 9000 patients.

DATA GOVERNANCE

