V	As in grade IV with presence of Mirizzi Syndrome type 2 or higher, cholecysto-cutaneous, cholecysto-duodenal or cholecysto-colic fistula		

Clavien-Dindo Classification System

Grade [30]	Definition (examples listed in italics)
I	
Any deviation from the normal postoperative course without the need for pharmacological (other than “allowed therapeutic regimens”), surgical, endoscopic or radiological intervention.
 
Allowed therapeutic regimens are: selected drugs (antiemetics, antipyretics, analgesics, diuretics and electrolyte replacement), physiotherapy and wound infections opened at the bedside but not treated with antibiotics.
 
Examples: Ileus (deviation from the norm); hypokalaemia treated with K; nausea treated with cyclizine; acute kidney injury treated with intravenous fluids.

II	
Requiring pharmacological treatment with drugs beyond those allowed for grade I complications. Blood transfusions and total parenteral nutrition are also included.
 
Examples: Surgical site infection treated with antibiotics; myocardial infarction treated medically; deep venous thrombosis treated with enoxaparin; pneumonia or urinary tract infection treated with antibiotics; blood transfusion for anaemia.

IIIa	
Requiring surgical, endoscopic or radiological intervention, not under general Anaesthetic (GA).
 
Examples: Therapeutic endoscopic therapy (do not include diagnostic procedures); interventional radiology procedures.

IIIb	
Requiring surgical, endoscopic or radiological intervention, under GA.
 
Examples: Return to theatre for any reason.

IVa	
Life-threatening complications requiring critical care management with single organ dysfunction, or neurological complications including brain haemorrhage and ischemic stroke (excluding TIA).
 
Examples: Single organ dysfunction requiring critical care management, e.g. pneumonia with ventilator support, renal failure with filtration; SAH; stroke

IVb	
Life-threatening complications requiring critical care management with multi-organ dysfunction.

V	
Death

Definition of Complications

Complication	Definition
Surgical site infection	Purulent drainage from the incision; OR At least two of: pain or tenderness; localised swelling; redness; heat; fever; AND the incision is opened deliberately to manage infection, or the clinician diagnoses a surgical site infection; OR Wound organisms AND pus cells from aspirate/ swab.

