Pulmonary complications [31]	Atelectasis OR pneumonia OR pulmonary aspiration OR acute respiratory distress syndrome
Bile leak	Grade A: bile leak which requires little or no change in the patient's management; resolves with conservative management within 1 week. Grade B: bile leak or collection which requires additional diagnostic or interventional procedures, such as ERCP or re-laparoscopy or Grade A bile leak which lasts more than 1 week. Grade C: Bile leak or collection which requires re-laparotomy.
Intra-abdominal abscess/collection	A clinical diagnosis of intra-abdominal collection (fever or abdominal pain or wound infection with dehiscence of any layer below fat/Scarpa's fascia) with operative or radiological evidence of a collection.
Acute pancreatitis [28]	Diagnosed using the revised Atlanta guidelines which state the diagnosis of acute pancreatitis requires two of the following three features: 
 Abdominal pain consistent with acute pancreatitis (acute onset of a persistent, severe, epigastric pain often radiating to the back) Serum lipase activity (or amylase activity) at least three times greater than the upper limit of normal Characteristic findings of acute pancreatitis on contrast-enhanced computed tomography.
Common bile duct injury [32-34]	Any injury to the main biliary tree will be classified using the Strasberg Classification System (see figure below): A – leak from cystic duct or small duct in liver bed B – occlusion of an aberrant right hepatic duct C – leak from an aberrant right hepatic duct D – lateral injury to the common hepatic or bile duct (<50% of circumference) E1 – transection or stricture of common hepatic or common bile duct >2cm from the hilum. E2 - transection or stricture of common hepatic duct <2cm from the hilum. E3 – Transection of the common hepatic duct at the level of the bifurcation without loss of contact between left and right hepatic duct. E4 – Transection of the common hepatic duct at the level of the bifurcation with loss of communication between the left and right hepatic duct. E5 – injury of a right segmental duct combined with an E3 or E4 injury.

Strasberg Classification System

American Joint Committee on Cancer (AJCC) 8th Edition TNM Stage

Category [35]	Definition
T category	
Tis	Carcinoma in-situ
T1a	Limited to the lamina propria
T1b	Invades the muscle layer
T2a	Invades the perimuscular connective tissue on the peritoneal side

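### Appendix D limits bile duct injury to the main biliary tree yet lists class A leaks as injuries, and no rule makes sites enter such a leak as an injury

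*Protocol*

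**What the plan says.** **Definition.** In Appendix D, Definition of Complications, the entry for common bile duct injury begins "Any injury to the main biliary tree will be classified using the Strasberg Classification System". The list of classes that follows starts with "A – leak from cystic duct or small duct in liver bed".

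**Bile leak.** The same table defines bile leak as a complication in its own right, graded A to C by the management it needs. It names no anatomical source and does not refer to Strasberg class A.

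**Forms.** In Appendices A and B, bile leak is a tick-all-that-apply complication recorded with a Clavien-Dindo grade only. BDI is a Yes/No item at 30 days and, if No, again at one year. The Strasberg grade and the other BDI fields are completed only after a Yes.

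**Comparator.** Audit Standards, Intra-operative, item 6b reads: "If considering all types of BDIs, rates are 0.4% and 0.8% for elective and emergency settings, respectively". Under Primary Outcome Measure, "The primary endpoint of this study is the compliance to pre-, intra-, and post-operative audit standards".

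**Mirizzi syndrome.** Under Exclusion Criteria, Indication, "Patients with Mirizzi syndrome should be excluded". The Nassar table in Appendix D describes grade V as "As in grade IV with presence of Mirizzi Syndrome type 2 or higher", or with certain fistulas.

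**The concern.** A cystic duct or liver-bed leak is an injury by the class list and not an injury by the opening phrase. A site that follows the opening phrase can answer BDI No, tick bile leak, and have completed the form properly. A site that follows the class list will answer BDI Yes, grade A. The protocol does not choose between them.

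The comparator covers all types of injury, so a numerator that loses class A at some sites is set against a rate that is meant to include it. Variation is to be examined across HDI groups, so a difference in reading could show up as a difference in injury rate. BDI matters here: assessing it is a secondary aim, it is one of the two reasons given for one-year follow-up, it enters the textbook outcome, and it is the only outcome cited in support of the sample size. The Data Validation section would not necessarily find the problem, because it checks two outcome measures that it does not name.

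**Working it through.** **The plan's own figure.** Data Analysis & Sample Size cites a guideline for at least 9000 patients, and gives no error rate, power, effect or precision. It can be neither reproduced nor refuted. Comparing 0.4% with 0.8% by n per group = [z(α)√(2p̄(1−p̄)) + z(β)√(p1(1−p1)+p2(1−p2))]² / (p2−p1)², one-sided 5%, 80% power, gives 4609 per group, or 9218. A one-sample test of 0.4% against 0.6%, two-sided 5%, 80% power, gives 8903. Both are near 9000, but on inputs the protocol does not state. Nothing below rests on this figure.

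**Can a missed class A leak be recovered?**
- Entered as BDI Yes: the Strasberg grade is present, and class A can be counted or set aside.
- Entered as bile leak only, BDI No: there is a Clavien-Dindo grade and no Strasberg grade. The source could be the cystic duct, the liver bed or another duct (classes C and D can also leak), so the record cannot be classified.

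**Effect on the rate.** Inputs from the protocol are p = 0.4% and 0.8% (item 6b) and N = 15,000 (anticipated sample). Assumed inputs are f, the share of all BDIs that are class A, and r, the share of class A leaks entered as BDI. The protocol gives neither.

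Recorded rate = p × [(1 − f) + f × r]. Results for p = 0.4% / 0.8%:

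| f | r = 0 | r = 0.5 | r = 1 |
|---|---|---|---|
| 25% | 0.30% / 0.60% | 0.35% / 0.70% | 0.40% / 0.80% |
| 50% | 0.20% / 0.40% | 0.30% / 0.60% | 0.40% / 0.80% |
| 75% | 0.10% / 0.20% | 0.25% / 0.50% | 0.40% / 0.80% |

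For scale, if all 15,000 patients were in one setting, 15,000 × 0.004 = 60 events, exact 95% interval 0.31% to 0.51%, and 15,000 × 0.008 = 120 events, interval 0.66% to 0.96%. With r = 0, the recorded rate is just outside these intervals at f = 25% and well outside at f = 50%.

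Between two groups with the same true rate, one entering every class A leak and the other none, the ratio of recorded rates is 1/(1 − f): 1.33 at f = 25%, 2 at 50% and 4 at 75%.

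**Mirizzi, checked separately.** If a share m of patients has Mirizzi syndrome with k times the BDI risk of the rest, the rate after excluding all of them is p / [(1 − m) + m × k]. From 0.4%: m = 0.1%, k = 5 gives 0.4/1.004 = 0.398%; m = 1%, k = 10 gives 0.4/1.09 = 0.367%; m = 2%, k = 20 gives 0.4/1.38 = 0.29%. Again m and k are assumptions. Only the last value leaves the interval above.

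**The case against.** **Class A is plainly a grade of injury.** It is a tick box on the case report form and in the data dictionary, and the BDI form lists bile leak among its presentations. A reader might infer that bile leak and BDI are conflicting definitions. They are not: they overlap, one patient may properly be entered under both, and the Yes/No item still counts that patient once. All of this stands. It shows what was probably intended, but it does not remove the opening phrase that says otherwise or supply a rule for entry.

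**The rates are not a threshold.** Item 6b describes rates and sets no limit, unlike the readmission standard. The protocol also says of some standards that "their attainment will not be considered mandatory or a potential definitive measure of quality in global cholecystectomy". This limits the consequence for the primary endpoint. It does not settle what is counted, and BDI is to be assessed in any case.

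**Class A can already be separated.** That is true for every injury entered as BDI, but not for a leak entered only as bile leak.

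**Mirizzi.** A reader might infer that Mirizzi syndrome found at operation is excluded, so that the hardest cases are lost. The unconditional sentence allows this, and the contrast with cancer, where "if gallbladder cancer is found unexpectedly during or after cholecystectomy (i.e. on histology), the patient should be included", supports it. But the sentence stands under Indication and gives no time of diagnosis, and grade V remains recordable. Grade V also covers fistulas, so it is needed whatever the Mirizzi rule and cannot identify Mirizzi cases. The protocol does not settle the matter. Nor would a uniform exclusion, before or during surgery, depend on access to imaging.

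**Conclusion.** The point holds as an internal contradiction in the BDI definition, joined to forms that cannot repair it afterwards. Comparability with the 0.4% and 0.8% rates, and between sites and HDI groups, is not assured.

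The stronger statement, that the rate is not comparable, is not supported. It would require knowing how the source of those rates treated class A, and how sites actually enter these leaks. The protocol shows neither. The figures are a sensitivity range: a true 0.4% recorded as 0.3% to 0.1% assumes a class A share of 25% to 75% and no class A leak entered as BDI. If half are entered, the range is 0.35% to 0.25%; if all are, there is no loss.

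The Mirizzi wording is a minor and separate inconsistency. Its effect on the rate is small unless both the frequency and the relative risk are assumed to be high.

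**What to change.** 1. In Appendix D, replace the opening phrase of the BDI entry with a definition as any Strasberg A-E injury.
2. Add a data-entry instruction to Appendix B: a leak from the cystic duct or liver bed is entered as BDI Yes, grade A, even if it is also ticked as bile leak, and is counted once as BDI.
3. Report A-E against the item 6b rates, and B-E separately.
4. Do not derive class A from the bile leak field. It has no anatomical source, so leaks of other classes would be miscounted as class A.
5. Reconcile the Mirizzi exclusion with Nassar grade V by stating how a case found at operation is handled. Limiting the exclusion to Mirizzi syndrome diagnosed before surgery is tempting but should be avoided: eligibility would then depend on access to pre-operative imaging, which may differ between the HDI groups being compared.

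The cost is a few sentences and no new form field. Records already entered with bile leak ticked and BDI No would need a query to the site, because the dataset alone cannot classify them.
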